4.1.1 Criteria for Calculation and Reporting of Area Under the Concentration-time Curve

The minimum requirement for the calculation of area under the concentration-time curve (AUC) will be the inclusion of at least 3 consecutive concentrations above the lower limit of quantification. If there are only 3 consecutive concentrations, at least 1 should follow C_{max} .

4.1.2 Criteria for Handling Missing or Concentrations Below the Limit of Quantification in Pharmacokinetic Analysis

Plasma concentrations below the limit of quantification (BLQ) will be assigned a value of 0 before the first measurable concentration and thereafter BLQs will be treated as missing. The following rules apply with special situations defined below:

- If an entire concentration-time profile is BLQ, it will be excluded from PK analysis.
- Where 2 or more consecutive concentrations are BLQ at the end of a profile, the profile will be deemed to have terminated and any further quantifiable concentrations will be set to missing for the calculation of the PK parameters, unless they are considered to be a true characteristic of the profile of the drug.

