12.4. Appendix 4 - Schedule of Assessments

Table 9: Schedule of Assessments

Period	Screening	Treatment							Washout / Follow-up			
Visit	1	2	3	4	5	6	7	8	9	10	TD	EoS
Day	-28 to -3	1 (predose)	11	31 (predose)	41	61 (predose)	71	91	101	121	-	170
Window			±2	±2	±3	±2	±3	±2	±3	±3		±10
Informed consent	X											
Medical history	X											
Drug & alcohol screen	X											
I/E criteria	X	X										
Physical Exam	X	X	X	X		X		X		X	X	X
Height	X											
Weight	X	X										X
Vital signs	X	X	X	X	X	X	X	X	X	X	X	X
12-lead ECG	X	X						X				X
HIV, Hepatitis B, Hepatitis C	X											
aPTT, Free and total FXI	X	X	X	X	X	X	X	X	X	X	X	X
aPTT (corrected for FXI), FXI:C		X				X		X				X
PK assessment: total MAA868		X	X	X	X	X	X	X	X	X		X
Antidrug antibodies (ADA)		X		X		X	X	X		X		X
Exploratory biomarker collection	X	X		X		X		X		X		
Complete safety Labs	X	X	X	X	X	X		X		X	X	X
Pregnancy test	Serum	Urine			Urine			Urine			Urine	Urine
Urine	X	X	X	X	X	X		X		X	X	X
Fecal occult blood test	X	X										
AE collection						X						
Concomitant meds						X						
Local assessment of CV and cerebrovascular events							X					
Local assessment of bleeding events							X					
Dispense Study Medications		X		X		X						
Drug Accountability		X		X		X		X				
MAA868		X		X		X						
Placebo		X		X		X						

Period	Screening	Treatment							Washout / Follow-up			
Visit	1	2	3	4	5	6	7	8	9	10	TD	EoS
Day	-28 to -3	1 (predose)	11	31 (predose)	41	61 (predose)	71	91	101	121	-	170
Window			±2	±2	±3	±2	±3	±2	±3	±3		±10
Injection site inspection (post-dose)		X	X	X	X	X	X					
Study disposition								X			X	X

TD = Study treatment discontinuation; EoS = End of Study; FXI:C = Factor XI coagulation activity

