4.1 Pharmacokinetic Analysis

PK samples will be obtained and evaluated at all post-screening visits (where data permit) in all subjects at all dose levels using the actual recorded sampling times. Untreated (placebo) samples will not be analyzed. All concentrations below the lower limit of quantitation (LLOQ) or missing data will be labeled as such in the concentration data listings.

The concentration-times courses of abelacimab will be tabulated for each sampling interval. Individual and geometric mean concentration vs time curves of MAA868 (using the actual sampling times for individual plots and the planned sampling intervals for mean plots) will be plotted using both linear and semilogarithmic scale.

The following pharmacokinetic parameters will be estimated, where data permit, from the plasma concentrations of total MAA868 following the Day 61 dose administration using noncompartmental methods in validated software program Phoenix WinNonlin (Certara, Version 8.1 or higher):

Parameter	Units ^a	Definition
AUC _{last}	h*µg/mL	area under the concentration-time curve from time 0 to the time of the last quantifiable concentration ^b
C _{max}	µg/mL	maximum observed concentration within the postdose concentration-time profile ^c
C _{min}	µg/mL	minimum observed concentration within the postdose concentration-time profile
DAUC _{last}	h*µg/mL/mg	AUC _{last} normalized by dose administered ^d
DC _{max}	µg/mL/mg	C _{max} normalized by dose administered ^d

^a Units are based on concentration units (provided by the bioanalytical lab or preferred units for presentation of PK parameters) and dose units used in the study.

^b Area under the concentration-time curve will be calculated using the linear trapezoidal rule for increasing and decreasing concentrations

^c Due to the sparse sampling, this may not directly correspond to the C_{max} of MAA868 determined with intensive sampling schemes.

^d Calculated by dividing the parameter by the dose (mg)

Additional PK parameters may be determined where appropriate.

CONFIDENTIAL

Page 10 of 28

Document Date: 18-MAR-2021

ST-AD-008 version 05

Statistical Analysis Plan

Sponsor Name: Anthos
Sponsor Protocol ID: ANT-004

Covance Study ID: 000000189471

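### AUClast after the Day 61 dose has no common interval and Cmax has no required sample, so missed visits can distort the descriptive PK summaries

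*SAP*

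**What the plan says.** SAP 4.1 estimates the PK parameters "from the plasma concentrations of total MAA868 following the Day 61 dose administration". AUClast is the "area under the concentration-time curve from time 0 to the time of the last quantifiable concentration", so each subject's own last usable sample sets its length. Cmax is the "maximum observed concentration within the postdose concentration-time profile". Both are also reported divided by dose (DAUClast, DCmax).

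SAP 4.1.1 gives the acceptance rule, for AUC only: "The minimum requirement for the calculation of area under the concentration-time curve (AUC) will be the inclusion of at least 3 consecutive concentrations" above the limit of quantification, and "If there are only 3 consecutive concentrations, at least 1 should follow" Cmax. It names no minimum span and no sample that must be present. Cmax has no acceptance rule. A footnote to the parameter table cautions: "Due to the sparse sampling, this may not directly correspond to the" Cmax that intensive sampling would give.

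In Protocol Appendix 4, Table 9, the row "PK assessment: total MAA868" is marked from the third dose onward at Day 61 (predose), 71, 91, 101, 121 and 170. It is not marked at the treatment-discontinuation visit. Under SAP 5.5, one PK/PD assessment is enough to enter the analysis set. SAP 7.9 and Table 1 summarise the parameters by dose group with arithmetic and geometric means.

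**The concern.** A mean of AUClast is interpretable only if the areas being averaged cover comparable time. Here the span depends on when a subject was last sampled, and the acceptance rule counts samples without asking which ones they are. Cmax depends on a single visit: Day 71 is the only scheduled sample between the third dose and the 30-day trough. If it is lost, the trough takes its place under the same label.

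Characterising PK is in the study title, and Protocol 1.2 says the results will help select the phase 3 dose. DAUClast and DCmax exist so that exposure can be read across 120 mg and 180 mg. If early departures or missed Day 71 visits were more common at one dose, that reading would shift for reasons unrelated to the drug.

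**Working it through.** **Spans.** SAP 2.2 gives 110 days from the last dose to end of study. By subtraction, 170 − 61 = 109 days, which agrees to within a day. The short profiles are:
- Days 61 predose, 71 and 91: 91 − 61 = 30 days. This passes when Cmax is at Day 71, because Day 91 then follows it.
- If the predose value does not count towards the three, Days 71, 91 and 101 are the shortest run that includes Day 71: 101 − 61 = 40 days.

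A 30-day span needs Days 101, 121 and 170 all absent or below quantification. Missing only Day 101 or only Day 121 leaves 109 days. Missing only Day 170 leaves 121 − 61 = 60 days.

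**A missed Day 71.** Five values remain (61 predose, 91, 101, 121, 170), so the AUC rule is met and its post-Cmax clause does not apply. The largest post-dose value left is Day 91.

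**Model for size (assumed).** One compartment, first-order absorption, linear PK, doses on Days 1, 31 and 61. Half-life is 20–28 days (Protocol 1.1). Tmax is 6–20 days after dosing, from the Day 7 to 21 in Protocol 1.1 with dosing on Day 1. Each dose contributes a concentration proportional to ka/(ka − ke) × [exp(−ke·t) − exp(−ka·t)], with ke = ln 2 / half-life and ka solved from ln(ka/ke)/(ka − ke) = Tmax. Areas use the SAP's linear trapezoid on the scheduled days.

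*One corner in full: half-life 20, Tmax 6.* Concentrations relative to Day 71:

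| Day | 61 | 71 | 91 | 101 | 121 | 170 |
|---|---|---|---|---|---|---|
| Relative concentration | 0.462 | 1.000 | 0.504 | 0.356 | 0.178 | 0.033 |

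The successive trapezoids are 7.31, 15.04, 4.30, 5.34 and 5.16, total 37.15.
- To Day 91: (7.31 + 15.04)/37.15 = 0.60.
- To Day 101: 26.65/37.15 = 0.72.

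*Across the whole range:*

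| Quantity | Range |
|---|---|
| 30-day AUClast / full-schedule AUClast, r | 0.454–0.601 |
| 40-day AUClast / full-schedule AUClast | 0.58–0.72 |
| Reported Cmax / true peak, Day 71 present | 0.90–1.00 |
| Reported Cmax / true peak, Day 71 missed | 0.46–0.82 |

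**Effect on a group of 12.** With k subjects cut at Day 91, the geometric mean falls by 1 − r^(k/12) and the arithmetic mean by k(1 − r)/12.

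| k | Geometric mean falls by | Arithmetic mean falls by |
|---|---|---|
| 1 | 4.2–6.4% | 3.3–4.6% |
| 2 | 8.1–12.3% | 6.7–9.1% |
| 3 | 11.9–17.9% | 10.0–13.7% |

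The values of k are illustrations; neither document gives a missed-visit rate.

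**Informal comparison between doses.** Take a true 180:120 ratio of 1.50 and k = 2 at one dose only. The geometric mean ratio becomes 1.50 × r^(2/12) = 1.315–1.378 if the cut subjects are at 180 mg, and 1.50 / r^(2/12) = 1.633–1.711 if they are at 120 mg. With equal truncation at both doses it stays at 1.50, although both means are low.

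**The case against.** The case on the other side has real force.

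- **The rule is more than any three samples.** The post-Cmax clause excludes a profile still rising at Day 91. It does not exclude Days 61, 71 and 91 with the peak at Day 71.
- **The AUC rule does not govern Cmax.** That gap comes from the Cmax definition in SAP 4.1, and the footnote partly discloses it. The footnote is a general warning, however: it neither withholds nor marks a value taken from Day 91.
- **The outputs are descriptive and partly protected.** Concentrations are summarised by visit and listed individually, individual curves are plotted, and SAP 4.1 allows additional parameters. A careful reader could spot a short profile, but the summary tables would not show it.
- **No objective is a PK parameter.** This stands and limits the consequence.

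A reader might go further and infer that the plan yields a biased dose ratio. The documents do not support that. No 180:120 ratio, proportionality model or test is planned, and an informal ratio moves only if missingness differs by dose. SAP 7.4 says COVID-19 disruptions will be listed; it predicts neither a rate nor a difference between cohorts. Nor does one missed visit produce a 30-day area: the three last samples must all be lost.

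**Conclusion.** The gap is real and modest. As written, AUClast values covering 30 or 40 days can be averaged with values covering 109 days, and a Day 91 value can be reported as Cmax after one missed visit. The summaries of AUClast, Cmax, DAUClast and DCmax can be distorted, as can any informal comparison of doses if missingness differs between them. Whether they will be is unknown.

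The sizes rest on the one-compartment model, linear PK and assumed numbers of affected subjects. Values below quantification late in follow-up could shorten AUClast too, perhaps more at 120 mg, but the limit of quantification is not given. Free FXI at Day 91, the primary endpoint, uses none of these parameters.

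**What to change.** In SAP 4.1 and 4.1.1:

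- Add AUC over the dosing interval Day 61–91, with its dose-normalised form, as the exposure measure summarised across doses. Calculate it only when the Day 61 predose, Day 71 and Day 91 samples are all available. Under linear PK the ratio between doses then stays at 1.50 whatever is missed after Day 91.
- Summarise Cmax and DCmax only for subjects with a Day 71 sample; list the others with a flag.
- Keep AUClast, but flag profiles that end before end of study for reasons other than values below quantification, and show the last sampling day. Dropping every such profile would leave completers only, in groups of 12, and is not recommended.

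The cost is SAP wording and the loss of a few subjects from individual PK parameter summaries. All the samples are already scheduled.

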4.1.3 Treatment of Outliers in Pharmacokinetic Analysis

If a value is considered to be anomalous due to being inconsistent with the expected PK profile, it may be appropriate to exclude the value from the PK analysis. However, the exclusion of any data must have strong justification and will be documented in the CSR.

4.2 Pharmacodynamic Variables

The following Pharmacodynamic (PD) parameters will be estimated:

- Free FXI
- Activated partial thromboplastin time (aPTT)
- Total FXI
- FXI coagulation activity (FXI:C)

CONFIDENTIAL

Page 11 of 28

PD parameters are used in the primary endpoint analysis. PD samples will be obtained and evaluated in all subjects at all dose levels. PD parameters aPTT, Free FXI, and Total FXI are collected at all visits. FXI coagulation activity is collected at day 1, day 61, day 91, and EoS. Concentrations of plasma total MAA868 (i.e., MAA868 that is bound to FXI or not bound to FXI) will be measured in plasma and determined by a validated LC-MS/MS method.

5. Analysis Populations/Sets

5.1 All Randomized Set

The all randomized set will include all subjects who are randomized.

5.2 Safety Set

The safety set will include randomized subjects who received at least one dose of study drug. Subjects will be analyzed based on the actual treatment taken.

5.3 Full Analysis Set (FAS)

The full analysis set will include all randomized subjects who had at least one dose of study drug and at least one post-baseline assessment. This set excludes subjects who are randomized into the study in error and did not receive study drug. Subjects will be analyzed based on the assigned treatment at the randomization.

5.4 Per Protocol Set

The per-protocol set will include subjects in Full Analysis Set that have no important protocol deviations after randomization.

Protocol deviations are defined as any change, divergence, or departure from the study design or procedures defined in the study protocol. Important protocol deviations are a subset of protocol deviations and may significantly impact the correctness, accuracy, and/or reliability of the study data or that may significantly affect a subject's rights, safety, or well-being.

5.4.1 Important Protocol Deviations Leading to Exclusion from the PP

Only those important protocol deviations considered to have a major effect on efficacy will lead to complete exclusion of the subject from the PP. For the purposes

Statistical Analysis Plan

Sponsor Name: Anthos
Sponsor Protocol ID: ANT-004

Covance Study ID: 000000189471

of this study, the list of subjects that have been identified as important protocol deviations leading to exclusion from the PP set is listed below. It is considered that the occurrences of any of these criteria might have an important influence on the primary efficacy endpoint.

Missed IMP dose

Missed FXI collection at V8, D91

Missed FXI collection at V2, Randomization

Out of window visit greater than 30 days

Most of the important protocol deviations leading to exclusion from the PP set require clinical or medical monitoring interpretation. These criteria will be reviewed prior to database lock. Important protocol deviations leading to exclusion from the PP set occurring during the study will be reviewed and approved by Anthos prior to database lock. Should additional important protocol deviations leading to exclusion from the PP set, not anticipated at the time of preparing this SAP, be identified during the study they will be documented in a SAP amendment and included in all relevant protocol deviation reviews and approvals.

5.5 PK/PD Analysis Set

The PK/PD analysis set will include all subjects who received at least one dose of study drug and have at least one PK/PD assessment.

6. Data Handling

6.1 Time points and Visit Windows

Day 1 is defined as the day subjects receive the first dose of study drug. Relative days after Day 1 are calculated as (assessment date – Day 1 date) + 1. Relative days prior to Day 1 are calculated as (assessment date – Day 1 date). The day prior to Day 1 is Day -1.

Baseline is defined as the most recent result obtained prior to first administration of study medication. This occurs at visit 2 (day 1 pre-dose). If the assessment is not performed at visit 2, the value from visit 1 (screening) will be used. If this value is not present, there will be no baseline value.

Trough FXI levels will only be used if they are considered "on treatment". A measurement is considered "on treatment" if it is collected within 30 (± 5) days after the last administration of MAA868.

CONFIDENTIAL

Page 13 of 28

Statistical Analysis Plan

Sponsor Name: Anthos
Sponsor Protocol ID: ANT-004

Covance Study ID: 000000189471

All data will be analyzed using nominal study visits as defined in the schedule of assessments and eCRF. Unscheduled visits will be listed but not tabulated. No visit windows will be applied for summary and analysis.

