7.7 Liver safety monitoring

To ensure subject safety and enhance reliability in determining the hepatotoxic potential of an investigational drug, a standardized process for identification, monitoring and evaluation of liver events must be followed.

Please refer to [Appendix 1](#) for complete definitions of liver events.

Follow-up of liver events

Every liver event defined in [Appendix 1](#) should be followed up by the Investigator or designated personnel at the trial site, as summarized below. Additional details on actions required in case of liver events are outlined in [Table 4](#) of Appendix 1.

- Repeating liver chemistry tests (ALT, AST, total bilirubin (TBL), PT/INR, ALP and γ GT) to confirm elevation as soon as possible

These liver chemistry repeats should always be performed using the central laboratory, with the results provided via the standard electronic transfer. If results are needed quickly then the repeats can also be performed at a local laboratory to monitor the safety of the subject. If a liver event is subsequently reported, any local liver chemistry tests previously

conducted that are associated with this event should be available to Covance and the Sponsor.

- If the initial elevation is confirmed, close observation of the subject will be initiated, including consideration of treatment interruption if deemed appropriate.
- Discontinuation of the investigational drug (refer to [Section 4.3](#) (Discontinuation of study treatment)), if appropriate
- Hospitalization of the subject if appropriate
- Causality assessment of the liver event
- Thorough follow-up of the liver event should include
 - Repeating liver chemistry tests two or three times weekly. Testing should include ALT, AST, ALP, PT/INR, and γ GT. If total bilirubin is elevated $> 2 \times$ ULN, fractionation into direct and indirect bilirubin is required. To rule out muscular origin of transaminase elevations, CPK should be measured along with liver chemistry tests. Frequency of retesting can decrease to once a week or less if abnormalities stabilize or the study drug has been discontinued and the subject is asymptomatic. Retesting should be continued up to resolution.
 - Obtaining a more detailed history of symptoms and prior or concurrent diseases.
 - Obtaining a history of concomitant drug use (including non-prescription medications and herbal and dietary supplement preparations), alcohol use, recreational drug use, and special diets.

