7.10 Clinical Laboratory Evaluations

Clinically relevant deviations of laboratory test results occurring during or at completion of the study must be reported and discussed with Covance personnel. The results should be evaluated for criteria defining an AE and reported as such if the criteria are met. Repeated evaluations are mandatory until normalization of the result(s) or until the change is no longer clinically relevant. In case of doubt, Covance personnel should be contacted.

Safety labs (hematology, clinical chemistry and urinalysis) do not need to be repeated at baseline if the Baseline visit is taking place within 48 hours of the screening labs being collected from an individual subject.

Subjects should be instructed to fast for at least 8 hours prior to scheduled safety lab collections.

Clinically notable laboratory findings are defined in [Appendix 3](#).

Hematology

Hemoglobin, hematocrit, red blood cell (RBC) count, white blood cell (WBC) count with differentials and platelet count will be measured.

Clinical chemistry

Sodium, potassium, creatinine, BUN/urea, uric acid, chloride, albumin, calcium, alkaline phosphatase, total bilirubin, bicarbonate/HCO₃, LDH, GGT, AST, ALT, CK, glucose, total

cholesterol, triglycerides. If the total bilirubin concentration is increased above 1.5 times the upper limit of normal, direct and indirect reacting bilirubin should be differentiated.

Urinalysis

Measurements for specific gravity, protein, glucose and blood will be performed. Microscopy, WBC, RBC and sediments will also be assessed in case of an abnormal test result.

Special clinical laboratory evaluations

Stool samples will be collected to check for occult blood at screening and baseline. Screening fecal samples can be collected at any time during the Screening period, and baseline fecal samples must be collected within 72 hours of Day 1. If fecal screening samples are collected within 72 hours of Day 1, then they do not need to be repeated for the Baseline visit. In the event that a subject is unable to produce a stool sample for sampling, the site medical staff may elect to produce a sample via digital extraction from the rectum.

Details regarding collection methods and processing are outlined in the Central Laboratory Manual.

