12.3. Appendix 3 - Clinical notable laboratory values

Clinical notable laboratory values:

The definition, the specific alert criteria and the corresponding actions for hepatic and renal notable laboratory abnormalities are respectively provided in [Appendix 1](#) and [Appendix 2](#).

The following laboratory values are considered clinically notable and should be forwarded to Covance at the same time that they are sent to Investigators:

- A change from baseline in hemoglobin ≥ 2 g/dL
- A decrease from baseline in platelets count $\geq 50\%$ or $< 100 \times 10^9/L$
- A positive fecal occult blood test
- Macroscopic hematuria

Whenever a clinically notable laboratory value is identified, a detailed subject history and examination are indicated to identify, document and potentially eliminate a bleeding event:

- Blood pressure assessment (after 5 min rest, with an appropriate cuff size);
- Signs and symptoms such as shortness of breath, tiredness, abdominal pain, hematemesis, rectorrhagia, melena, gingival or nose bleeding, bruising and hematoma;
- Concomitant events or procedures such as trauma, surgical procedures.

When one of the above occurs the action plan is as follows:

- Confirm the value, assess and document the clinically notable laboratory value in the CRF or via electronic data load;
- Investigate the underlying causes such as clinical or subclinical bleeding event and the contributing factors such as intake of prohibited medications;
- Monitor subject regularly (frequency at Investigator's discretion) until resolution or stabilization. Hospital admission, additional laboratory tests, endoscopy, volume replacement, transfusion, etc. should be performed at the Investigator's discretion and according to the medical needs (see [Section 6.3](#) for reversal therapy).

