7.8.3 Laboratory Evaluations

Data for hematology, blood chemistry, and urinalysis analytes received from central laboratory/recorded in the eCRF will be listed and summarized by treatment group and overall for each scheduled collection visit. Standard descriptive statistics (see [Table 1](#)) will be presented for the observed values and change from baseline. Baseline definition can be found in [section 3.1](#).

A laboratory value that is within the central laboratory's reference range will be considered normal. A laboratory value that is outside the central laboratory's normal range will be considered abnormal and will be flagged as either high (H) or low (L). The number and percentage of subjects with abnormal laboratory values will be summarized for each analyte for each scheduled visit. Shift tables will be presented to display the shift in the normal range categories (low, normal, high) from baseline to each post-baseline visit for the following laboratory evaluations: hemoglobin, hematocrit, prothrombin time, activated partial thromboplastin time, total bilirubin, alkaline phosphatase, aspartate aminotransferase (AST), alanine aminotransferase (ALT), and creatinine.

Additionally, the number and percentage of subjects with clinically significant laboratory values will be summarized for each analyte for each scheduled visit.

The following analytes will be included in the analysis:

Statistical Analysis Plan

Sponsor Name: Anthos
Sponsor Protocol ID: ANT-004

Covance Study ID: 000000189471

Hematology	Serum Chemistry	Urinalysis (dipstick)
Hemoglobin	Sodium	Specific Gravity
Hematocrit	Potassium	Protein
Red Blood Cell Count	Creatinine	Glucose
Platelets	Blood Urea Nitrogen	White Blood Cell Count
Neutrophils	Uric acid	Red blood Cell Count
Lymphocytes	Chloride	
Monocytes	Albumin	
Eosinophils	Calcium	
Basophils	Alkaline phosphatase	
Leukocytes	Total Bilirubin	
Activated Partial Thromboplastin Time (aPTT) -FSL	Direct Bilirubin*	
Prothrombin Time (PT)	Indirect Bilirubin*	
International Normalized Ratio (INR)	Bicarbonate	
	Lactate Dehydrogenase (LDH)	
	Gamma-Glutamyltransferase (GGT)	
	Aspartate aminotransferase (AST)	
	Alanine aminotransferase (ALT)	
	Creatine Kinase (CK)	
	Glucose	
	Total Cholesterol	
	Triglycerides	

*if Total Bilirubin >1.5x upper limit of normal

All clinical laboratory data will be presented in listings. Laboratory data will be summarized in SI units.

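### Peak and nadir laboratory values from unscheduled draws enter no laboratory table, and the protocol's laboratory alert thresholds are never counted by subject

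*SAP*

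**What the plan says.** **Visit rule.** SAP 6.1 sets the basis for all output: "All data will be analyzed using nominal study visits as defined in the schedule of assessments and eCRF". It then says: "Unscheduled visits will be listed but not tabulated".

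**Laboratory tables.** SAP 7.8.3 plans four kinds of summary.
- Descriptive statistics: the data "will be listed and summarized by treatment group and overall for each scheduled collection visit".
- Flags against the reference range: "The number and percentage of subjects with abnormal laboratory values will be summarized for each analyte for each scheduled visit".
- Clinical significance: "Additionally, the number and percentage of subjects with clinically significant laboratory values will be summarized for each analyte for each scheduled visit".
- Low/normal/high shifts from baseline to each later visit, for nine analytes. Platelets are not among them.

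All laboratory data are also listed, and SAP Table 1 places unscheduled visits in the listings in date order.

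**Repeat draws.** Protocol 7.7 asks, for liver events: "Repeating liver chemistry tests two or three times weekly". Protocol 7.10 adds: "Repeated evaluations are mandatory until normalization of the result(s) or until the change is no longer clinically relevant". Appendix 2 asks for a repeat within 24–48 hours, if possible, after a creatinine rise of 50% or more. Appendix 3 treats "A change from baseline in hemoglobin" of at least 2 g/dL as notable and asks for confirmation.

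**Thresholds.** Appendices 1 to 3 define numerical alerts for ALT/AST, bilirubin, INR, ALP, creatinine, haemoglobin and platelets. No SAP table counts them.

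**The concern.** The protocol creates off-schedule draws mainly when a value is already abnormal, and those are the results that SAP 6.1 keeps out of the tables. For an anticoagulant antibody with a half-life of 20 to 28 days, a safety reader wants each subject's worst haemoglobin, platelet and liver value, and wants to know how many subjects crossed a threshold that the protocol itself calls notable. The planned laboratory tables answer neither question. SAP 3.2 names laboratory parameters among the secondary safety endpoints, so the gap touches a stated endpoint.

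**Working it through.** The plan gives no figure on this point, so the main check is to set the planned outputs side by side.

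**1. Which outputs can hold a value from an unscheduled draw?**

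| Output | Basis | Unscheduled value included? | Alert threshold counted? |
|---|---|---|---|
| Descriptive statistics (SAP 7.8.3) | scheduled visit | no | no |
| High/low counts (7.8.3) | scheduled visit | no | no, reference range only |
| Clinically significant counts (7.8.3) | scheduled visit | no | no |
| Shifts (7.8.3) | each post-baseline visit, under the 6.1 rule | no | no |
| TEAE tables (7.8.2) | event start date | only if recorded as an AE | no |
| Bleeding table (7.8.8) | adjudicated event | only if a suspected bleed | no |
| Listings | all visits | yes | not a count |

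**2. What the tables can show at scheduled visits.** A high flag covers 1.1 × ULN and 9 × ULN alike. The by-visit maximum shows one extreme per group, not how many subjects crossed a threshold. Tables by single analyte cannot show the combined potential Hy's law criterion (ALT or AST above 3 × ULN with bilirubin above 2 × ULN and no initial ALP rise above 2 × ULN).

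**3. What can pass through the remaining routes.** Protocol 7.6.1 makes a laboratory abnormality an AE only if it causes signs or symptoms, is judged clinically significant, or needs therapy. The middle test is a judgement; the Appendix 1 to 3 cut-offs are numerical. For asymptomatic ALT/AST above 3 and up to 5 × ULN, Table 5 asks only for monitoring, without the liver-event CRF step given for the higher bands. If such a value is also not judged to be an AE, its size appears in no table. Even when an AE is recorded, the TEAE tables give preferred term and severity, not multiples of ULN or grams of haemoglobin.

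**4. How many draws the rule can set aside.** Post-baseline safety laboratory days in Table 9 are 11, 31, 41, 61, 91, 121 and 170. The gaps from Day 1 are 10, 20, 10, 20, 30, 30 and 49 days (total 169). If liver retesting ran at two to three draws a week through a whole gap:
- 30-day gap: 30/7 × 2 = 8.6 to 30/7 × 3 = 12.9, so about 9 to 13 draws.
- 49-day gap: 49/7 × 2 = 14 to 49/7 × 3 = 21 draws.

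These are upper figures, because Protocol 7.7 lets the frequency fall to weekly or less once values stabilise, or once the drug is stopped and the subject has no symptoms.

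**5. Scale of one subject.** With 12 active subjects per cohort (Protocol 5.3), one case is 1/12 = 8.3%. The exact Clopper-Pearson 90% method reproduces the SAP 2.3 example (11/12: 0.661 to 0.996). The same method gives:
- 0/12: 0 to 1 − 0.05^(1/12) = 22.1%.
- 1/12: 0.4% to 33.9%.

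This is the weight of a single subject, not an expected loss.

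**The case against.** A reader might infer that these values are missing from every safety table, or that an affected subject would look normal throughout. The documents do not support that.
- Clinically significant, symptomatic or treated abnormalities are AEs, and Protocol 7.6.1 points investigators to the Appendix 1 to 3 ranges when identifying them. The TEAE tables go by onset date, so it does not matter which draw found the abnormality.
- An overt bleed with a haemoglobin fall of 2 g/dL or more is a major bleed (Appendix 5). A suspected bleed with a fall but no overt bleeding is classed as no bleeding event. Both have rows in SAP 7.8.8, though without the haemoglobin value.
- Most of the cited repeats confirm or follow an abnormality already found. If a scheduled draw found it, the subject is already in the by-visit counts, and what is lost is the height of the peak. For ALT/AST above 8 × ULN, Table 5 asks for causality assessment and liver-event CRFs, so such a case is unlikely to go unreported.
- All values are listed, and about 48 subjects can be read individually.

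A reader might also infer that the MAA868-versus-placebo comparison understates risk. The same rule applies in every arm, no significance tests are planned, and nothing shows that loss would differ between arms. Nor do the gaps between visits measure loss: with no draw in a gap, there is no value for any table to recover. The 49-day gap also lies 60 to 109 days after the Day 61 dose, in washout.

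Finally, the current protocol's Section 8.6 (Clinical Laboratory Evaluations) counts abnormal values by scheduled visit and plans no alert table, so the SAP does not depart from it.

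All of this stands, and it narrows the point. It does not supply a subject-level count of threshold crossings or a worst-value summary.

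**Conclusion.** The point holds in a limited form. Peaks and nadirs from unscheduled draws are absent from every laboratory table. They reach a safety table only through AE reporting or bleeding adjudication, and otherwise appear only in listings. Separately, the protocol's numerical alerts are not counted even at scheduled visits. The weakness is shared by protocol and SAP.

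Its size cannot be estimated from the documents, which give no rate of off-schedule abnormalities; one subject weighs 8.3 percentage points in an arm of 12. The conclusion assumes that repeat tests outside the Table 9 visits are recorded as unscheduled. No primary result changes. The change is worth making because the present rule gives a poorer safety summary than the collected data allow.

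**What to change.** 1. In SAP 6.1, restrict the exclusion of unscheduled results to by-visit summaries.
2. Add a table by treatment group with the count and percentage of subjects whose worst post-baseline value at any time meets each criterion below. Use scheduled, unscheduled and TD results, and local results where they are in the database (Protocol 7.7 asks only that local results be available to the CRO and sponsor).
   - ALT or AST above 3, 5 and 8 × ULN
   - ALT or AST above 3 × ULN with INR above 1.5 (INR is in the SAP 7.8.3 analyte list)
   - the combined potential Hy's law criterion
   - ALP above 2 × ULN
   - creatinine up by 25% and by 50%
   - haemoglobin change of 2 g/dL or more
   - platelets down by 50% or more, or below 100 × 10^9/L
3. For combined criteria, state how close in time the components must be; Appendix 1 does not say.
4. Add a shift from baseline to worst post-baseline value, and include platelets.
5. Leave out criteria with no planned post-baseline laboratory source (urine protein- and albumin-creatinine ratios, fecal occult blood) and those that need clinical signs.

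The cost is SAP wording and one or two extra tables. No new assessments are needed.
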